This document is a clinical investigational plan (CIP) for the AmplatzerTM Post-Infarct Muscular Ventricular Septal Defect (PIVSD) Occluder Humanitarian Device Exemption (HDE) Post Approval Study (H070005). This clinical study is intended to evaluate the safety and probable benefit of the AmplatzerTM PIVSD Occluder in transcatheter closure of muscular ventricular septal defects subsequent to acute myocardial infarction. This clinical study is sponsored by Abbott.

This study will be conducted in accordance with the CIP. All parties involved in the conduct of the study will be qualified by education, training or experience to perform their tasks and training will be documented.

2 Background and Justification for Clinical Study

Muscular ventricular septal defect is an uncommon and life-threatening complication of myocardial infarction, which results in significant morbidity and mortality. Post-myocardial infarction muscular ventricular septal defect (post-MI VSD) occurs in <1% of patients who experience a myocardial infarction. When left untreated it can result in rapid clinical deterioration characterized by cardiogenic shock and end-organ dysfunction with subsequent fatality. Standard practices and procedures used for the treatment of a post-infarct ventricular septal defect include one or more of the following:

- Medical Therapy Use of pharmacological therapy, such as vasodilators, to decrease left-toright shunt associated with the defect, may increase cardiac output and stabilize the patient hemodynamically. However, vasodilators may be precluded in patients with severe cardiogenic shock. Inotropic agents and vasopressors, which may be used as alternatives to vasodilators, have the disadvantage of markedly increasing left ventricular work and myocardial oxygen consumption. The mortality rate of using medical therapy alone exceeds 90%.²
- Mechanical Circulatory Support Use of an intra-aortic balloon pump or a temporary ventricular
 assist device to support the circulatory system to recovery or as a bridge to additional therapy,
 such as a longer term mechanical circulatory support device or cardiac transplantation.
 Mortality rate using this approach is approximately 17%.³
- Surgical Repair Use of open cardiac surgery under cardiopulmonary bypass to repair the ventricular septal defect. Operative mortality rate ranges between 19% and 54%.⁴

Although open cardiac surgery may be used to repair a post-infarct VSD, many patients, particularly those in cardiogenic shock and with end-organ injury, may be poor candidates for surgery. Furthermore, patients who have significant residual shunting after open cardiac surgical repair may be at high risk for reoperation. The AmplatzerTM PIVSD Occluder is a minimally invasive alternative to achieving VSD closure in patients who are not satisfactory candidates for open surgical repair.

This confidential document is the property of Abbott and shall not be reproduced, distributed, disclosed or used without the express written consent of Abbott.

Template: 86357 Rev. F Page 4 of 26

Clinical Investigation Plan

FDA issued a Humanitarian Device Exemption (HDE) approval order for the Amplatzer PIVSD Occluder (H070005) on January 10, 2017. The Conditions of Approval require that Abbott conduct a post approval study to evaluate the safety and probable benefit of the AmplatzerTM PIVSD Occluder.

[figure not shown]
3 Device under Study

3.1 Identification and Description of the Devices under study

3.1.1 Identification

The Amplatzer[™] Post-infarct Muscular VSD Occluder is illustrated in **Figure 1**, and a listing of the devices to be included in this PAS appears in **Table 1**.

Figure 1: Amplatzer™ Post Infarct Muscular VSD Occluder

- A. Disc diameter
- B. Device size (at waist)
- C. Marker bands
- D. Waist length
- E. Delivery cable connector
- F. Distal (left ventricular) disc
- G. Proximal (right ventricular) disc

Table 1: Identification of Devices under Study

DEVICE NAME	MODEL*	WAIST DIAMETER (DEVICE SIZE)	DISC DIAMETER	WAIST LENGTH	REGULATORY STATUS
Amplatzer™ PIVSD Occluder	9-VSDMPIHDE-016	16 mm	26 mm	10 mm	HDE Designation
Amplatzer™ PIVSD Occluder	9-VSDMPIHDE-018	18 mm	28 mm	10 mm	HDE Designation
Amplatzer™ PIVSD Occluder	9-VSDMPIHDE-020	20 mm	30 mm	10 mm	HDE Designation
Amplatzer™ PIVSD Occluder	9-VSDMPIHDE-022	22 mm	32 mm	10 mm	HDE Designation
Amplatzer™ PIVSD Occluder	9-VSDMPIHDE-024	24 mm	34 mm	10 mm	HDE Designation

^{*}Model numbers for subjects may reflect the pre-HDE designation of 9-VSDMPIIDE-016, -018, -020, -022, and -024

3.1.2 Device Description and Intended Purpose

The Amplatzer™ PIVSD Occluder is intended for percutaneous transcatheter closure of post-myocardial infarct muscular VSDs in patients who are not satisfactory surgical candidates. The occluder is implanted percutaneously to close post-myocardial infarct muscular VSD.

This confidential document is the property of Abbott and shall not be reproduced, distributed, disclosed or used without the express written consent of Abbott.

Template: 86357 Rev. F Page 5 of 26

Clinical Investigation Plan

The implant procedure is performed using a transcatheter approach under general anesthesia or conscious sedation, and can be performed in a catheterization laboratory setting under fluoroscopic and echocardiographic guidance.

The Amplatzer™ PIVSD Occluder is a self-expanding, double-disc device made from nitinol wire mesh (Figure 1) and designed to facilitate occlusion of muscular VSDs that occur post-myocardial infarction. The discs are linked together by a waist corresponding to the size of the VSD. To increase its closing ability, the discs and waist are filled with polyester fabric that is sewn securely to the device with polyester thread. Radiopaque marker bands at each end of the device provide visualization under fluoroscopy.

The Amplatzer™ PIVSD Occluder is designed to accommodate the damaged muscular tissue of the septal wall of myocardial infarction patients, and is available in five sizes: 16 mm, 18 mm, 20 mm, 22 mm, and 24 mm. All five device sizes have the same waist length of 10 mm.

The Amplatzer[™] TorqVue[™] system, which is 510(k) cleared, is used to deliver the Amplatzer[™] PIVSD Occluder. The delivery system consists of a delivery sheath with Touhy-Borst hemostatic adapter, dilator, loader, plastic vise, and delivery cable. A 9 Fr sheath is recommended for the 16 mm and 18 mm PIVSD occluders, and a 10 Fr sheath is recommended for the 20 mm, 22 mm, and 24 mm PIVSD occluders.

3.1.3 Device Handling and Storage

Consult the User's Manual for instructions for use, storage and handling instructions, preparation for use and any precautions.

The sponsor requires all products to be stored according to the labeling and Instructions for Use in a secure area to prevent unauthorized access or use.

3.2 Device Accountability

Device accountability independent of the study is required for the Amplatzer™ PIVSD Occluder since it is designated as a Humanitarian Use Device (HUD). As defined in 21 CFR 814.3(n), an HUD is a medical device intended to benefit patients in the treatment or diagnosis of a disease or condition that affects or is manifested in not more than 8,000 individuals in the United States per year. As part of post approval obligations, Abbott will annually report to FDA the number of devices shipped or sold since initial HDE marketing approval (21 CFR 814.126(b)(1)(iii)). If that number exceeds 8,000 then Abbott will provide an explanation.

4 Clinical Study Design

4.1 Clinical Study Design

This is a multi-center, observational study to evaluate the safety and probable benefit of the Amplatzer™ PIVSD Occluder for use in transcatheter closure of muscular ventricular septal defects following a myocardial infarction in the post approval setting.

As described in section 4.2, this study has five endpoints (safety: acute and chronic survival; effectiveness: technical success, acute and chronic closure). Two cohorts will be utilized to obtain study endpoint data. Cohort 1 will be comprised of all available Emergency and Compassionate PIVSD Occluder subject data from 2011 until the end of 2016 and these data will be used to determine technical success, acute survival, and chronic survival.

Template: 86357 Rev. F Page 6 of 26

Clinical Investigation Plan

[figure not shown]
[figure not shown]

Table 1: Estimated Timeline of Milestone Events

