5.1 Informed Consent Process

Cohort 1

A fully executed informed consent form is required prior to each Emergency and Compassionate PIVSD procedure. These previously executed procedure consent forms contain language that allows for Sponsor data collection. The Sponsor will verify that an executed consent form is present and covers the access and use of stored data for research analysis prior to utilizing a subject's data for the analysis of the endpoints.

Cohort 2

For living subjects, the Principal Investigator or his/her authorized designee will conduct the Informed Consent process (this retrospective group may include re-consenting previously implanted Emergency and Compassionate Use patients or those implanted with the approved HUD), as required by applicable regulations and the center's IRB. This process will include a verbal discussion with the subject or legally authorized representative on all aspects of the clinical study that are

Template: 86357 Rev. F Page 8 of 26

Clinical Investigation Plan

relevant to the subject's decision to participate (or the legally authorized representative's decision to consent), such as details of data to be collected, anticipated benefits, and potential risks of clinical study participation. During the discussion, the Principal Investigator or his/her authorized designee will avoid any improper influence on the subject and will respect the subject's legal rights. The subject or legally authorized representative shall be provided with the informed consent form written in a language that is understandable to the subject or legally authorized representative and has been approved by the center's IRB. The subject or legally authorized representative shall have adequate time to review, ask questions, and consider participation.

If the subject or legally authorized representative agrees to participate, the Informed Consent form must be signed and dated by the subject or the subject's legally authorized representative and by the person obtaining the consent. The signed original will be filed in the subject's hospital or research charts, and a copy will be provided to the subject or the subject's legally authorized representative.

The Principal Investigator or his/her authorized designee will document the informed consent process in the subject's hospital and/or research charts. The date of signature will be entered on the applicable Case Report Form (CRF).

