5.3.2 Implant/Procedure and Post-Procedure

The following procedure information will be collected retrospectively via each subject's medical records:

- Date of procedure (if multiple procedures occurred, date of each procedure)
- Procedure success in a subject
- Implanted device(s) model number(s)
- Post-procedure echocardiogram obtained immediately after the successful deployment of the device and up to 7 days post-procedure is evaluable and can be sent to the echocardiography core laboratory for residual shunt evaluation.

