8.3 Complaints

The investigator will be responsible for reporting complaints involving the Amplatzer™ PIVSD Occluder for implant procedures that occur following HDE approval on January 10, 2017.

The investigator must notify the Abbott Postmarket Surveillance Department by emailing the information on the device to [contact] or calling [contact] as soon as possible after becoming aware of the complaint.

Template: 86357 Rev. F Page 16 of 26

Clinical Investigation Plan

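### Does the post-approval wording in section 4.1 misdescribe estimates that rest on implants made before approval?

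*Combined protocol and SAP*

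**What the plan says.** Section 4.1 describes a multi-center observational evaluation of the occluder "for use in transcatheter closure of muscular ventricular septal defects following a myocardial infarction in the post approval setting". It continues: "Cohort 1 will be comprised of all available Emergency and Compassionate PIVSD Occluder subject data from 2011 until the end of 2016", and it gives those data three endpoints: technical success, acute survival and chronic survival. Sections 4.4 and 5.3 repeat this. Section 2 supplies the date that matters: "FDA issued a Humanitarian Device Exemption (HDE) approval order for the Amplatzer PIVSD Occluder (H070005) on January 10, 2017".

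Section 4.4 gives Cohort 2 the two closure endpoints and chronic survival. Entry requires age over 18, a previous successful implant and a post-procedure echocardiogram that the core laboratory can evaluate, plus consent if the subject is living. Section 5.1 says of this cohort that "this retrospective group may include re-consenting previously implanted Emergency and Compassionate Use patients or those implanted with the approved HUD". The footnote to the device table in section 3.1.1 agrees: "Model numbers for subjects may reflect the pre-HDE designation of 9-VSDMPIIDE-016", and so on for the other four sizes.

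Section 6.1 states that no hypotheses are tested. The only subgroup analysis shown (section 6.4) is by sex.

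**The concern.** Taken literally, the phrase in section 4.1 promises evidence on use after approval, and two endpoints cannot give it. They are also the two that concern attempted implants: acute survival is defined from an attempt, and technical success is the outcome of one. Cohort 2 cannot fill the gap, because it admits only subjects whose implant succeeded. On the text shown, no post-approval estimate covers all attempts.

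For closure and chronic survival the worry is different: pre- and post-approval implants may be mixed in unstated proportions, with no split by period. Yet the sponsor treats the approval date as a meaningful cut elsewhere. Section 8.3 requires complaint reports "for implant procedures that occur following HDE approval on January 10, 2017".

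The HDE conditions of approval require the study, and section 11 sends endpoint summaries to FDA. A reader who took the phrase at face value could mistake results from Emergency and Compassionate use for performance of the device after approval.

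**Working it through.** The plan states no figure to reproduce on this point. The check compares dates, traces each endpoint to its cohort, and then asks what a split by period would yield.

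**Dates.** The last possible Cohort 1 day is December 31, 2016 (section 4.1). Approval is January 10, 2017 (section 2). The gap is 10 days, so Cohort 1 contains 0 post-approval implants.

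**Endpoints by source** (sections 4.1 and 4.4):

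| Endpoint | Source | Post-approval share |
|---|---|---|
| Technical success | Cohort 1 | 0% |
| Acute survival | Cohort 1 | 0% |
| Acute closure | Cohort 2 | 0% to 100%, not fixed in the text shown |
| Chronic closure | Cohort 2 | 0% to 100%, not fixed in the text shown |
| Chronic survival | Cohorts 1 and 2 | below 100% if any Cohort 1 subject is pooled |

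The factual claim therefore holds: 2 of 5 endpoints are wholly pre-approval, and 3 of 5 may be mixed.

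**Does this contradict the plan's stated purpose?** Section 1 identifies the document as the plan for an HDE post approval study, and section 2 says the conditions of approval require one. In that context the phrase can be read as the study's regulatory label. The objective in section 4.2 concerns patients implanted after an acute myocardial infarction and names no period, so both cohorts serve it. The sentence in section 4.1 that gives the Cohort 1 dates also names its endpoints. The contradiction exists only if the phrase is read as a restriction on implant date, and the rest of the plan does not read it that way.

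**What would a split at the approval date show?** The documents as shown give no cohort sizes, so the stratum sizes and the 80% closure rate below are assumptions. The exact (Clopper-Pearson) 95% interval for x successes in n runs from the 2.5% point of Beta(x, n − x + 1) to the 97.5% point of Beta(x + 1, n − x). For 183-day survival without censoring, Greenwood's variance reduces to S(1 − S)/n. It is largest at S = 0.5, so the half-width is at most 1.96 × √(0.25/n).

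| n in stratum | Closure at 80%: exact 95% interval | Survival: largest half-width |
|---|---|---|
| 10 | 44.4% to 97.5% | 31.0 points |
| 20 | 56.3% to 94.3% | 21.9 points |
| 30 | 61.4% to 92.3% | 17.9 points |
| 50 | 66.3% to 90.0% | 13.9 points |

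For two strata of 20, both at 80%, the approximate half-width for the difference is 1.96 × √(2 × 0.8 × 0.2/20) = 1.96 × 0.1265 = 24.8 points. Only a very large period effect would be visible.

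**Would such a split be interpretable?** For closure it would be imprecise but coherent. For chronic survival it would not be clean. The pre-approval stratum would include Cohort 1, which is entered on an attempt. The post-approval stratum could come only from Cohort 2, which is entered on success plus an evaluable echocardiogram. Period and selection would be confounded. Stratifying by date of first successful implant would also leave failed Cohort 1 attempts with no date.

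**The case for a change.** The strongest case for a change is that it costs almost nothing. Section 5.3.2 already collects procedure dates and model numbers, Cohort 1 is pre-approval by definition, and a label with one count would remove any doubt. The sentence in section 4.1 also ties the phrase to use of the device, so a literal reading is not perverse. Nothing shown obliges the final report to carry the cohort dates over to the estimates.

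Part of this stands. The wording is loose, and a count of Cohort 2 implants before and after approval would be informative. But the label would restate what section 4.1 says and sections 4.4 and 5.3 repeat. The caveat that Cohort 2 results depend on successful implantation and an evaluable echocardiogram follows from its entry criteria in sections 4.4 and 5.2. The feared misreading requires a report that omits the plan's own description of its data. An analyst following the plan would name the cohort beside each estimate anyway, since the endpoints are assigned by cohort.

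The case for split analyses is weaker. Section 7.3 reports no device modification or recall bearing on safety or clinical performance, and the table footnote in section 3.1.1 treats the older model numbers as an earlier designation of the same five sizes. These facts do not prove that results are constant over time, since patients and operators may change, but the documents offer no ground for expecting a difference.

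Finally, the point about Cohort 2 rests largely on what the public copy does not show: the rest of section 4.1, the body of the timeline table and sections 6.2 and 6.3. An implant window, a cohort size or a rule for combining cohorts could be there. That absence cannot be counted against the plan.

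**Conclusion.** No change to the plan is called for. Technical success and acute survival describe pre-approval Emergency and Compassionate use, with 0 post-approval implants, and Cohort 2 may mix periods. The plan discloses both facts, and neither biases an estimate for the cohort it is assigned to. What remains is a loose phrase with a natural regulatory reading, and a reporting detail that the collected dates allow an analyst to supply.

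Splitting closure and survival by period would be a trade-off with little gain: wide intervals at the assumed stratum sizes of 10 to 50, and a survival comparison confounded with how Cohort 2 is selected.

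The conclusion rests on reading the phrase alongside the title, the unrestricted objective and the stated cohort dates. It also assumes that the final report identifies the cohort behind each estimate. The documents give no figure for a difference between periods, so no effect on results can be sized.

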4.2 Objective

The objective of this clinical study is to evaluate the safety and probable benefit of the PIVSD Occluder in patients undergoing implantation of the PIVSD Occluder following an acute myocardial infarction.

4.2.1 Effectiveness Endpoints

Technical Success: Technical success occurs when a subject is successfully implanted with a PIVSD device in the ventricular septal defect. An implant attempt occurs when the delivery system is inserted in the subject's vasculature.

Acute Closure: Acute closure is defined as the absence of a residual shunt ≥3 mm, and will be assessed based on an echocardiogram obtained immediately after the successful deployment of the device and up to 7 days post-procedure.

Chronic Closure: Chronic closure is defined as the absence of a residual shunt ≥3 mm at 6 months or later.

4.2.2 Safety Endpoints

Acute Survival: Acute survival is defined as survival for at least 24 hours following an attempted PIVSD device implant.

Chronic Survival: Chronic survival is defined as survival for at least 183 days post-procedure.

Template: 86357 Rev. F Page 7 of 26

Clinical Investigation Plan

4.3 Implanter Training

The study is expected to enroll subjects who have been implanted with a PIVSD Occluder; therefore no implanter training is planned under this CIP.

4.4 Study Population

The intended population for the Amplatzer™ PIVSD Occluder is patients with post-myocardial infarct muscular VSD who are not satisfactory surgical candidates. The study will enroll subjects in two cohorts:

Cohort 1: All available Emergency and Compassionate PIVSD Occluder subject data from 2011 until the end of 2016 will be utilized to determine technical success, acute survival, and chronic survival. All subjects belonging to this cohort must have undergone an attempt to close a post-infarct VSD using the Amplatzer™ PIVSD Occluder.

Cohort 2: This cohort will consist of subjects over the age of 18 years who have previously been successfully implanted with the PIVSD Occluder and:

- for living subjects, the subject or subject's legally authorized representative has provided consent to participate in this study.
- the subject's post-procedure echocardiogram is evaluable and can be sent to the echocardiography core laboratory for residual shunt assessment.

Therefore, this cohort will be composed of retrospectively enrolled subjects. This cohort will be utilized to determine acute and chronic closure, and chronic survival.

5 Procedures

Approval from the Sponsor must be received prior to initiating study procedures. Baseline, procedure, post-procedure, and six month subject data will be collected retrospectively on each subject. The following sections provide a detailed description of procedures required by this CIP.

5.1 Informed Consent Process

Cohort 1

A fully executed informed consent form is required prior to each Emergency and Compassionate PIVSD procedure. These previously executed procedure consent forms contain language that allows for Sponsor data collection. The Sponsor will verify that an executed consent form is present and covers the access and use of stored data for research analysis prior to utilizing a subject's data for the analysis of the endpoints.

Cohort 2

For living subjects, the Principal Investigator or his/her authorized designee will conduct the Informed Consent process (this retrospective group may include re-consenting previously implanted Emergency and Compassionate Use patients or those implanted with the approved HUD), as required by applicable regulations and the center's IRB. This process will include a verbal discussion with the subject or legally authorized representative on all aspects of the clinical study that are

Template: 86357 Rev. F Page 8 of 26

Clinical Investigation Plan

relevant to the subject's decision to participate (or the legally authorized representative's decision to consent), such as details of data to be collected, anticipated benefits, and potential risks of clinical study participation. During the discussion, the Principal Investigator or his/her authorized designee will avoid any improper influence on the subject and will respect the subject's legal rights. The subject or legally authorized representative shall be provided with the informed consent form written in a language that is understandable to the subject or legally authorized representative and has been approved by the center's IRB. The subject or legally authorized representative shall have adequate time to review, ask questions, and consider participation.

If the subject or legally authorized representative agrees to participate, the Informed Consent form must be signed and dated by the subject or the subject's legally authorized representative and by the person obtaining the consent. The signed original will be filed in the subject's hospital or research charts, and a copy will be provided to the subject or the subject's legally authorized representative.

The Principal Investigator or his/her authorized designee will document the informed consent process in the subject's hospital and/or research charts. The date of signature will be entered on the applicable Case Report Form (CRF).

Failure to obtain informed consent from a subject prior to clinical study enrollment should be reported to Sponsor within 5 working days and to the reviewing center's IRB according to the IRB's reporting requirements.

